## 5.0 Procedures Involved

### 5.1 Study Design:

The study is a clinic-randomized trial of EHR clinical decision support tools for pain treatment and opioid prescribing. We propose clinic-level randomization in order to minimize the potential for spillovers or “contamination” of the intervention across the study arms.

The randomization plan is described in the figure below. There are two dimensions to the randomization. One dimension is treatment arm within a factorial study design: some clinics will be randomized to receive “care as usual,” (Arm 1), some clinics will be randomized to receive Intervention set A (Arm 2), some clinics will be randomized to receive Intervention B (Arm 3), and some clinics will receive both Interventions A and B (Arm 4). The other dimension to randomization occurs among the clinics that are assigned to Intervention set A or B, and involves those clinics being randomized to three different conditions. 1) The clinic receives the intervention set for the entire 12 month study period (Subarm A), 2) the clinic receives the intervention set for only the first 6 months of the study period, and then reverts to “care as usual,” for Intervention set A and PMP integration without the reminder function for Intervention B (Subarm B), or 3) The clinic receives the intervention set for the first 6 months, but in the second 6 months, Intervention set A will only fire in a random half of clinical encounters and the reminder function will only fire in a random half of clinical encounters for Intervention B (Subarm C).

Exhibit 7. Randomization plan

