#### 5.5 Modifications to Procedures in Response to Data Monitoring Committee recommendations:

The external Data Monitoring Committee reviewed the results of the interim outcomes analysis (see Section 17.1 for details). Their letter to the PI is now added to the study IRB files. We will follow their recommendations and implement two changes to the study procedures.

Change #1: Open up the PMP Integration arm to the entire study population at the 6-month mark.

Change #2: We will not implement the secondary randomization of the intervention arm clinics into three subgroups. Instead, the clinics assigned to the “choice architecture” intervention set in Arms 3 and 4 will stay the same for months 6-12 of the study period.

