#### *Primary Outcome Analysis*

To test our primary hypotheses, we will fit mixed effects logistic regression models using data from the 12-month pre-intervention period, and the post-intervention period prior to any second-stage randomization (the model for the current “high risk” opioid group will be multinomial logistic regression due to the 3-category outcome). All models will include fixed effects for whether the encounter was at an intervention arm clinic, an indicator for whether the measurement was after the interventions began, and their interaction. The interaction is the primary measure of the intervention effect. These models include random effects for clinic and PCP (nested in clinic) to account for within-clinic and within-provider correlation. Because of the cluster-randomized design with a moderate number of clinics, residual imbalances in patient and PCP-characteristics among the randomized groups may exist. The primary analysis model will adjust for characteristics at all levels of the hierarchy including clinic-level (indicators for the four systems), PCP-level (clinician type [MD/DO, NP, or PA], sex, and length of tenure in medicine), and patient-level (age, sex, race/ethnicity, insurance status, and in-person or virtual visit). Separate models will be fit to assess the PDMP integration and choice architecture intervention and for the opioid-naïve and current, high-risk opioid users. In each model, the intervention group pools across two arms of the factorial design (e.g., the choice architecture intervention pools across arms 2 and 4) and the control condition pools across the remaining two groups (e.g., arms 1 and 3 to continue the example). A Bonferroni correction will adjust inference for multiple comparison across two different populations (opioid naïve and current, high-risk opioid users) but we will not adjust for multiple tests across the two different interventions.

As an exploratory analysis, we will assess whether PCP characteristics (clinician type and tenure in medicine) and patient characteristics (age, sex, and race/ethnicity) moderate the interventions’ effect. Tests for treatment effect heterogeneity will be implemented by adding the interaction between the potential moderator and the intervention indicator to the models for the primary

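### The final models for a 2×2 factorial leave out the other randomised intervention: no bias on average, but chance imbalance is missing from the standard error and no A×B estimate is planned

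*Combined protocol and SAP*

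**What the plan says.** Section 5.1 sets up the design: "One dimension is treatment arm within a factorial study design". Arm 1 is usual care, Arm 2 gets Set A, Arm 3 gets Set B and Arm 4 gets both.

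Section 17.3 (Primary Outcome Analysis) says "Separate models will be fit to assess the PDMP integration and choice architecture intervention", and "In each model, the intervention group pools across two arms of the factorial design". For choice architecture, that is arms 2 and 4 against arms 1 and 3. The treatment terms are given by "All models will include fixed effects for whether the encounter was at an intervention arm clinic, an indicator for whether the measurement was after" the start of the interventions, plus the product of the two, which is the effect measure. Adjustment is for health system, PCP and patient characteristics. On clustering: "These models include random effects for clinic and PCP (nested in clinic) to account for within-clinic and within-provider correlation".

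The other intervention is not among the covariates. Nor is it among the moderators: "we will assess whether PCP characteristics (clinician type and tenure in medicine) and patient characteristics (age, sex, and race/ethnicity) moderate the interventions’ effect". Three other places bear on the point:

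- Section 17.3 also plans descriptive outcomes and monthly trend graphs by study arm.
- Section 17.1 describes an interim model that has study-month indicators and appears, in a garbled sentence, to carry a term for receiving both interventions.
- Section 5.5 records a later change: "Open up the PMP Integration arm to the entire study population at the 6-month mark". It also cancels the second-stage randomisation.

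**The concern.** The plan justifies covariate adjustment by the moderate number of clinics and the residual imbalance that this may leave. It then omits the one clinic-level factor that the trial itself introduces to change prescribing. Two things are at stake.

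First, clinics are the unit of allocation and visits are the unit of analysis. Equal numbers of clinics per arm do not guarantee that the same share of visits is exposed to B in A and non-A clinics. The model has no B × post term and no clinic-by-period random effect, so any such imbalance moves the A estimate without widening its standard error.

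Second, A and B may not add up. Section 4.1 has the Set A alert fire when an opioid order is initiated, and the PMP reminder fire when it is being signed, so both act on the same order. If their effects overlap, the pooled figure describes neither A alone nor A on top of B, and no planned estimate would show that.

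**Working it through.** **1. The plan's own figure.** Exhibit 8 assumes a 7% control rate; section 17.2 gives 48 clinics in four equal arms, 10 providers per clinic, a six-month comparison and two-sided alpha 0.05. Section 17.3 adds a 12-month pre-period. For a difference in differences in which clinic and PCP effects cancel, the variance of one clinic's change in log odds at 30 visits per month is

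1/(10×30×12×0.07×0.93) + 1/(10×30×6×0.07×0.93) = 0.0128.

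With k clinics per side, SE = √(2×0.0128/k). At k = 12 this is 0.0462. A 15% reduction is a log odds ratio of 0.174, so power = Φ(0.1737/0.0462 − 1.96) = 96.4%, against 96% stated. At 15 visits the result is 75.8%, against 76% stated. All eight cells reproduce. This is 12 v 12 clinics, not the pooled 24 v 24 contrast of section 17.3; for that contrast SE = 0.0327 (30 visits) or 0.0462 (15 visits).

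**2. Equal clinics.** The design is orthogonal, so adding B × post leaves the SE for A at 0.0327. In simulation with no true A effect, mean error was −0.0001. Type I error was 5.2% and 4.4% (B cutting prescribing by 15% and 30%), identical with and without B.

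**3. Unequal clinics.** Assumption: lognormal clinic volumes with CV 0.4, 0.7 or 1.0, allocated without balancing on volume, and no clinic-by-period variance. Weighted analysis of 48 clinic-level differences, 30 visits per month, no true A effect, 6,000 runs per setting:

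| CV | B cuts 15%, B omitted | B cuts 30%, B omitted | B × post included |
|---|---|---|---|
| 0.4 | 6.3% | 9.4% | 4.7–5.3% |
| 0.7 | 7.8% | 19.9% | 5.1–5.2% |
| 1.0 | 11.3% | 28.3% | 4.8–5.4% |

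Separate runs together span about 5–11% and 9–29%. Mean error was about zero at every CV.

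Hand check: at CV 0.4 the share of visits exposed to B differs between A and non-A clinics with SD 0.057. For a 30% B effect (log odds ratio 0.379) the true SD of the A estimate is about √(0.0327² + (0.379×0.057)²) = 0.0392. The rejection limit is then 1.96×0.0327/0.0392 = 1.63 true SDs, or about 10%. At 15 visits the sampling SE is larger and the inflation smaller: √(0.0462² + 0.0216²) = 0.0510 gives a limit of 1.78, or about 7.6%.

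**4. Interaction.** The pooled log odds ratio is about the mean of the two simple ones. If A cuts prescribing by 30% without B and by nothing with B, the odds ratios are 0.685 and 1.000, and the model reports exp(−0.379/2) = 0.827. If A is −15% without B and +15% with B, it reports 0.989. Both cases are hypothetical.

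The SE of A × B × post is 2×0.0327 = 0.0653. Power for an interaction as large as a 15% reduction is Φ(0.1737/0.0653 − 1.96) = 75.8% at 30 visits and 46.8% at 15. For half that size it is 26.4% and 15.4%.

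**5. Months 7–12, if used.** Half the clinics have B in months 1–6 and all have it in months 7–12, so the weights without and with B become 25/75. The first example would read exp(−0.25×0.379) = 0.910. Coding B as on everywhere from month 7 with only a single post indicator does not solve this. On balanced cell means (12 pre, 6 + 6 post months), 80% of any common shift in months 7–12 is assigned to B; A is unaffected.

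**The case against.** Pooling two arms against two is the standard main-effects analysis of a factorial, and section 17.3 states it openly. Section 17.2 assumes equal allocation, so the other factor is balanced by design. A reader might infer that B's effect systematically leaks into A's estimate. The documents do not support that: the mean error is about zero, and with equal clinics there is no inflation either. What stands is chance imbalance that the standard error does not show.

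The size of that problem rests on inputs outside the documents. The clinic-size CV is assumed. No balancing on volume is described, but the randomisation figure (Exhibit 7) is not visible, and balancing would shrink the inflation. The largest figures need both a 30% effect of B and a CV of 0.7 or more.

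A reader might also infer that a mixed effect would be hidden. That goes too far: outcomes and trends are to be shown by arm, and the interim model may carry a both-interventions term. What is missing is an estimate with a confidence interval in the final analysis.

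Finally, one might infer that opening PMP integration to all clinics has already changed what the primary A contrast means. Section 17.2 places the Primary Aim in months 1–6, before that change. Section 17.3 ends the window at a second-stage randomisation that section 5.5 cancels, so the end date needs stating; but dilution follows only if later months enter.

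**Conclusion.** The point holds as a correctable weakness in model specification, not as a bias. The final primary models omit the other randomised factor and plan no A×B estimate. With Exhibit 8 inputs at 30 visits per month, nominal two-sided alpha 0.05, no clinic-by-period variance and an assumed CV of 0.4–1.0, type I error for A is about 5–11% or 9–29% for a B effect of 15% or 30%. Including B × post returns it to about 5%. By symmetry the same applies to the B model when A is omitted. If clinic-by-period variance exists, B × post alone will not restore 5%, and the interaction power above is optimistic. Under interaction the pooled result is an average whose components the plan shows only descriptively.

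**What to change.** For each population, fit one model with A, B, post, A × post and B × post, keeping the planned covariates and random effects. Take the two main-effect contrasts from it, and use the same structure for the EHR secondary outcomes. State the primary window as months 1–6, before PMP integration opens to all clinics. If months 7–12 are used, code B by period and add study-month indicators, as the interim model has, so that secular change is not credited to B.

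Pre-specify A × B × post with its confidence interval, and the effect of each intervention with and without the other, as supportive only. State that the primary contrast will not be switched in the light of the interaction result. Say clearly whether the interim model contains the both-interventions term, and explain any difference from the final model.

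Cost: a few lines in the plan and no new data. The B terms are a free improvement, with no loss of precision when clinics are of equal size. The supportive interaction is cheap, but its standard error is about twice that of the pooled effect, so a wide interval should not be read as showing that the interventions do not interact.

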### Futility Analysis

There will be no formal futility analyses presented to the DMC. Given that these interventions have small potential adverse effects, the DMC will NOT be asked to recommend early termination for futility.

17.2 Power Analysis: The proposed design has sufficient power to detect clinically meaningful changes in opioid prescription practices from the main effects of the two interventions and the control group (10). All power calculations assume a two-sided test at the 0.05 significance level. Power for the Primary Aim (comparison of intervention arms to the control during months 1-6) is shown in Exhibits 2a-b assuming a total of 48 clinical are randomized (equal allocation between Arms 1-4) with a conservative estimate of 10 providers per clinic (~12 providers per clinic in the FHS/UMP system). The range of the number of visits eligible and the percentage of visits with an opioid prescription in the control arm (for both the opioid-naïve and opioid-using populations) were based on preliminary data from the EHR from a subset of clinics that will be randomized. Meeker et al. (1) assumed an intra-clinic correlation of 0.05 but that encounters within the same provider were not further correlated. We assumed the correlation for visits within the same clinic (but with different providers) was 0.025 and the within-provider correlation would be 0.075 as well as considering a more conservative scenario (correlation given on the logistic scale (11)). We assumed a 5% and 17% prescription rate in the control arm for the opioid-naïve and opioid-using populations, respectively, based on preliminary analysis of opioid prescribing in Fairview primary care clinics, and based on published research (12). We considered a difference in the percentage of eligible encounters with an opioid prescription between the intervention and control groups of 3.5% and 5% to be of clinical interest in the two populations. Exhibits 8 and 9 demonstrate that we have sufficient power across a wide range plausible scenarios and maintain adequate power even under smaller effect sizes. These calculations are also conservative as they assume 48 clinics, whereas we expect to enroll over 50 clinics.

We also have sufficient power to detect differences between 2.5 to 4 percentage points across the two intervention sets during the first 6 months of the intervention.

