Exhibit 8. Power to detect a difference in proportion of eligible visits with an opioid prescription between intervention and control arms. Power calculations assume an opioid prescription rate in the no intervention arms of 7%.									
30 eligible visits/month/provider					15 eligible visits/month/provider				
	% reduction in opioid prescribing					% reduction in opioid prescribing			
Intra-clinic/ Intra-provider correlation	15%	20%	25%	30%	Intra-clinic/ Intra-provider correlation	15%	20%	25%	30%
0.025/0.075	96%	100%	100%	100%	0.025/0.075	76%	95%	100%	100%

Exhibit 9. Power to test a difference in proportion of eligible visits resulting in an opioid prescription between intervention and controls arms in opioid-using population (Primary Aim). Power calculations assume 40 clinics randomized equally to Arms 1-4 with 10 providers/clinic, the opioid prescription rate in the control arm was 17%.									
10 eligible visits/month/provider					5 eligible visits/month/provider				
	Difference in opioid prescription rate between control and intervention					Difference in opioid prescription rate between control and intervention			
Intra-clinic/ Intra-provider correlation	4.5%	5%	5.5%		Intra-clinic/ Intra-provider correlation	4.5%	5%	5.5%	
0.025/0.075	81%	89%	95%	0.025/0.075		77%	86%	93%	

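### Holm's step-down rule would keep the familywise guarantee of the planned Bonferroni correction across the two populations and recover some power

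*Combined protocol and SAP*

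**What the plan says.** Section 17.3 (Primary Outcome Analysis) fits separate models for each intervention in each population: opioid-naïve patients and current high-risk users. On multiplicity it states that "A Bonferroni correction will adjust inference for multiple comparison across two different populations" and that "we will not adjust for multiple tests across the two different interventions". Each intervention therefore has its own family of two primary tests. No step-down, gatekeeping or alpha-recycling rule appears anywhere, and no reason is given for the single-step form.

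Section 17.3 does not state the total level. Section 17.2 says "All power calculations assume a two-sided test at the 0.05 significance level", so its powers are at the unadjusted level. They are for the "comparison of intervention arms to the control during months 1-6".

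The Interim Outcome Analysis Plan in 17.1 sets Pocock-type Lan-DeMets boundaries for the primary endpoint. It spends one-sided 0.0155 at the interim and 0.0095 at the end, with decisions based on the opioid-naïve population only.

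**The concern.** Single-step Bonferroni holds both populations at 0.025 whatever happens in the other. A p-value of 0.03 in one population is then non-significant even when the other population's test has clearly succeeded. Holm's procedure tests the smaller p-value at 0.025 and, only if that succeeds, the larger at 0.05. It needs no assumption about how the two tests are correlated, which is useful here because the same clinics and clinicians supply both populations.

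What is at stake is power, not validity. The populations are parallel components with their own primary outcomes (sections 1.1 and 3.1), so a missed finding in either one matters. Because 17.2 computes power at 0.05, the exhibits do not show what the correction costs.

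**Working it through.** **1. Levels.** Two tests per intervention. Taking the total as two-sided 0.05 from 17.2, Bonferroni gives 0.05/2 = 0.025 each. The critical values are 1.960 (0.05) and 2.241 (0.025).

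**2. Reproducing the plan's power.** The Exhibit 9 inputs are 10 providers per clinic, a 17% control rate and 6 months of visits. For the correlations, "We assumed the correlation for visits within the same clinic (but with different providers) was 0.025 and the within-provider correlation would be 0.075", with "correlation given on the logistic scale". The residual variance is π²/3 = 3.290 and the total is 3.290/(1 − 0.075) = 3.557. The clinic variance is 0.025 × 3.557 = 0.0889 and the provider variance is 0.050 × 3.557 = 0.1778.

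For a 5-point difference at 10 visits a month, with 10 control and 30 intervention clinics:
- per-clinic variance, control: 0.0889 + 0.0178 + 1/(600 × 0.17 × 0.83) = 0.1185
- per-clinic variance, intervention: 0.0889 + 0.0178 + 1/(600 × 0.12 × 0.88) = 0.1225
- standard error: √(0.1185/10 + 0.1225/30) = 0.126
- log odds ratio: 0.407
- power: Φ(0.407/0.126 − 1.960), about 89.7% (stated 89%)

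All six cells come within 2 points: 81.5/89.7/95.0% against the stated 81/89/95%, and 77.5/86.5/92.8% against 77/86/93%. A 20 v 20 split, which is the pooled contrast of 17.3 with 40 clinics, does not reproduce them (90.8/96.0/98.5% at 10 visits). Exhibit 8 was not fully reproduced: a pre/post contrast with 12 v 12 clinics matches 7 of 8 cells and gives 73.6% against the stated 76%. The stated powers are therefore used as inputs below.

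**3. Power at 0.025.** For a stated power P at 0.05, δ = 1.960 + z(P), and power at 0.025 is B = Φ(δ − 2.241).
- P = 0.89: Φ(3.187 − 2.241) = 0.828
- P = 0.95: Φ(3.605 − 2.241) = 0.914
- P = 0.76: B = 0.665
- P = 0.77: B = 0.676

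**4. Power under Holm.** With independent tests, Holm power = B + B(other) × (P − B). For current users at 89% and opioid-naïve at 95%: 0.828 + 0.914 × (0.890 − 0.828) = 0.885.

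| Stated current-user power at 0.05 | Bonferroni | Holm, opioid-naïve 76% | Holm, opioid-naïve 95% |
|---|---|---|---|
| 77% | 67.6% | 73.9% | 76.2% |
| 81% | 72.5% | 78.1% | 80.3% |
| 86% | 78.8% | 83.6% | 85.4% |
| 89% | 82.8% | 86.9% | 88.5% |
| 93% | 88.4% | 91.4% | 92.6% |
| 95% | 91.4% | 93.8% | 94.7% |

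The 76% and 95% are the Exhibit 8 entries for 15% and 20% reductions at 15 visits a month. The gain runs from 2.4 points (93.8 − 91.4) to 8.6 points (76.2 − 67.6). It is 8.7 points if the opioid-naïve entry is 96%. In the 89%/95% case, a correlation between tests of 0.3 or 0.6 changes 88.5% to 88.1% or 87.8%. If the opioid-naïve population has no effect, Holm gives 0.828 + 0.025 × 0.062 = 0.829, almost no gain.

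**5. Error rates.**
- Both nulls true, independent tests: 1 − 0.975² = 4.94% under either rule.
- One null true: 2.5% under Bonferroni. Under Holm it is 0.025 + 0.025 × B(other), which is 4.2% for B = 0.665 and 4.8% for B = 0.914.
- Holm's bound is 5% in every configuration and under any dependence.

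**6. Interim boundaries.** The 17.1 table spends 0.0155 + 0.0095 = 0.025 one-sided. A Bonferroni share would be 0.0125 one-sided, and 0.0155 at the interim already exceeds it. The table's total fits only Holm's second step.

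**The case against.** Bonferroni is valid, prespecified and simple, and the plan applies it to inference rather than to tests alone. It gives simultaneous intervals that always agree with the decisions; Holm does not. Preferring that agreement to some extra power is a defensible choice, and this part stands.

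A reader might infer that the planned rule buys no protection at all against false positives. That goes too far. The guaranteed bound is the same, but with exactly one true null the realised error is 2.5% under Bonferroni and 4.2 to 4.8% under Holm in the cases above.

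A reader might also judge the loss by the chance of confirming both populations. With the weakest cell of each exhibit (76% and 77%) and independent tests, that chance is 45% under Bonferroni (0.665 × 0.676) and 58% under Holm. The documents do not make success in both populations a criterion; section 1.1 describes separate analyses. That pairing is also the least favourable available. Section 17.2 names 5 points as the difference of interest in current users, where Exhibit 9 gives 86 to 89%. For the opioid-naïve it names 3.5 points, half of the 7% base rate in Exhibit 8 and beyond its largest column (30%), where stated power is 100%. With opioid-naïve power near 100%, Holm returns current-user power to about its stated value, a gain of 86 − 78.8 = 7.2 or 89 − 82.8 = 6.2 points.

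Finally, the exhibits power a prescription proportion, not the three-category taper outcome, and Exhibit 9 does not match the pooled contrast of 17.3. The power figures can therefore show only rough size. None of this removes the ordering: Holm never rejects less and has the same 5% bound.

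**Conclusion.** The point holds as an inexpensive gain in efficiency. The planned correction is not an error, and nothing in the documents supports reading it as one. Holm keeps the guaranteed 5% familywise error and adds roughly 2 to 9 points of power per population on the stated exhibit powers. At the plan's own 5-point difference in current users the gain is about 6 to 7 points if the opioid-naïve effect is strong. It goes to whichever population has the larger p-value, and only when the other succeeds at 0.025.

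The assumptions are a total two-sided level of 0.05, exhibit powers taken as stated, and independent tests for the arithmetic. The familywise guarantee needs no independence. Two matters must be settled under either rule: the missing single p-value for the multinomial outcome, and the interim boundaries that spend the full level.

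**What to change.** In 17.3, replace the Bonferroni sentence with:

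> For each intervention, the two population-level primary p-values (for current high-risk users, one joint test of the intervention-by-period interaction terms in the multinomial model) will be tested by Holm's procedure at familywise two-sided 0.05; 97.5% confidence intervals will be reported.

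Add a footnote that a 97.5% interval may include the null for a hypothesis rejected at the second step.

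Reconcile this with 17.1. The final boundary cannot simply be recomputed at whichever level Holm assigns. The interim spend of 0.0155 is above the 0.0125 first-step share, and section 5.5 shows that the monitoring committee has already reviewed the interim results. The plan should state how the interim spend counts against the opioid-naïve test. The same statement is needed if Bonferroni is kept.

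The change needs no new data or models, and it should be entered before final results are known. Beyond the text and the reconciliation, it costs a higher actual error when exactly one null is true (from 2.5% to at most 5%) and occasional disagreement between an interval and a second-step rejection.
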